DICOM	Digital Imaging and Communications in Medicine
PI	Primary Investigator
IRB	Institutional Review Board
AIC	Advanced Imaging Center

1.0 Project Summary/Abstract

Currently men with elevated prostate specific antigen (PSA) or abnormal digital rectal examination (DRE) undergo systematic sampling of the prostate with transrectal ultrasound (TRUS)-guided needle biopsies. PSA and DRE have low specificity for prostate cancer (PCa), and TRUS biopsies have an approximately 30% false negative rate. Whether a quantitative detection specific magnetic resonance imaging (MRI) protocol improves PCa detection in biopsy naïve men is not adequately studied.

This pilot study aims to test a novel detection specific MRI protocol which uses image collection and post-processing to assist the radiologist find areas of the prostate with increased suspicion for clinically significant cancer. Men with an MRI negative for cancer will undergo standard of care TRUS biopsies, and men with suspicious MRI lesions (as defined by our preliminary data) will undergo biopsies of these lesions in addition to systematic TRUS biopsies. We will compare the yield of significant PCa between systematic sampling and MRI determined areas of the prostate.

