The PI-RADS has several limitations including modest inter-rater reliability(13, 14), and a false positive rate of as high as 88% of the PI-RADS 3 (indeterminate) scores (figure 1). Currently the same prostate MRI protocols are used for PCa detection in men with prior negative TRUS biopsies, staging of known PCa, and for suspected PCa local recurrence after treatment. As such, the protocol contains several imaging sequences such as T1 weighted imaging to detect hemorrhage related to biopsy and DCE which is of limited value for PCa detection which add to the study time and cost(15). In addition, the fields of view of prostate MRI protocols are designed to show surrounding structures such as the pelvic lymph nodes for staging purposes which aren't applicable to the primary PCa detection setting. These larger fields of view come at the expense of longer study times, and lower imaging detail in the prostate.

Finally, current prostate MRI protocols are designed for qualitative assessment and PI-RADS scoring. A detection specific protocol can be designed so that quantitative parameters can be measured as an adjunct to PI-RADS scoring. We hypothesize that quantitative tools for image assessment could benefit radiologists to further characterize indeterminate MRI studies, and to facilitate comparisons across patients, centers, and populations.

Our study explores 2 ways to improve mpMRI for PCa detection: 1) Developing an imaging protocol specifically designed for biopsy naïve men with suspected PCa and 2) improving utility of the collected images with quantitative image analysis tools as an adjunct to PI-RADS. DWI characterizes the Brownian movement of water molecules in tissues. Conventional DWI fits a line to data acquired using two strengths (b-values) of the magnetic diffusion gradient, the slope of which is the apparent diffusion coefficient (ADC) which can be used as a quantitative parameter.

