When compared to RP histology, ADC has a moderate inverse correlation with PCa grade (ref ADC and grade). With conventional DWI the calculation of ADC assumes a gaussian distribution of water molecule diffusion and tissue homogeneity which may oversimplify water motion in organs with complex tissue structures. A technique that more accurately determines water diffusion through tissues may better discriminate cancer grade. As such, we have tested stretched exponential (SEM) and kurtosis models of DWI with high b-values to determine the grade of PCa in 31 men undergoing biopsy targeted to MRI lesions identified using standard PI-RADS scoring. We found accuracy as measured by area under the receiver operator curve (AUC) that is significantly improved over PI-RADS, the PBCG model, and modestly improved over conventional ADC (Figure 2). Therefore, we propose to prospectively use quantitative DWI as a biomarker to determine regions of the prostate suspicious for high grade PCa in biopsy naïve men.

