3.0 Objectives/Aims

This study aims to determine whether a detection specific MRI protocol with quantitative image analysis can improve high grade PCa detection in men with clinical suspicion and no prior biopsy.

Aim 1: Design a PCa detection specific MRI protocol which will facilitate quantitative image analysis and reduce study time by ~50%

Current prostate mpMRI protocols include image sequences and fields of view outside of the prostate gland and its immediate surrounding that are not useful for PCa detection. We will create a detection specific MRI protocol featuring: smaller fields of view zoomed to the prostate, T2 weighted imaging at multiple echo times, chemical exchange saturation transfer imaging (CEST), and DWI at higher b values (up to 4000) that will allow for quantitative prediction of high grade PCa. The exact imaging acquisition parameters can be found in Appendix 3. We expect this MRI protocol to

reduce study (acquisition) time from approximately 45 minutes to 27 minutes, which will potentially lower cost and improve tolerance of the procedure. Significantly, we will omit DCE which will reduce the imaging time, and the risks associated with intravenous contrast including systemic fibrosis, and patient discomfort.

Aim 2: Determine the accuracy of the novel MRI protocol for detection of high grade PCa

50 men with clinical suspicion of PCa (elevated PSA and/or abnormal DRE) will be enrolled into a prospective protocol and will undergo detection protocol MRI described in Aim 1. Quantitative image analyses will be performed to generate SEM maps of DWI. Areas of suspicion for high grade PCa (GS ≥ 7) will be targeted for biopsy. Men with MRI with no areas of suspicion for high grade PCa will undergo standard of care 12 core TRUS biopsy. The primary endpoint will be the rate of detection of high grade PCa on the per patient and per biopsy core basis. Men with biopsy pathology negative for PCa will undergo standard of care (SOC) continued monitoring.

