5.0 Study Design and Procedures

This will be a single arm prospective clinical trial. Men with clinical suspicion for PCa but no prior prostate biopsy will be enrolled from the UI Health Urology clinics. All eligible men will be screened and enrolled by the clinical research coordinator. Enrolled men will undergo detection protocol MRI at the UIC Advanced Imaging Center (AIC) prior to diagnostic biopsy. The image acquisition parameters are listed in the Appendix 3. The MRI will be processed by the study team and evaluated for areas suspicious for high grade PCa by a board certified clinical radiologist ([name]). Subjects with MRI with no suspicious areas for high grade PCa will undergo SOC 12 core TRUS biopsy. Subjects with MRI suspicious for high grade PCa will have 2-4 biopsies guided toward each suspicious lesion using MRI/TRUS fusion biopsies (maximum of 12 cores). All biopsies will undergo SOC histologic processing and interpretation in pathology. Biopsy results will be communicated to the patients by the Urologist performing the biopsy and all additional management will be SOC. This visit will signify the end of the study. See the study schema in Figure 4.

[figure not shown]

Figure 4: Study schema

The primary outcome will be the rate of detection of high grade PCa on a per-patient and per biopsy core basis. The detection rate will be compared between patients with and without evidence of high grade PCa (GS ≥ 7) based on the detection protocol MRI. Secondarily we will analyze the accuracy of the individual MRI parameters including: T2 imaging, ADC, the SEM parameters (DDC and α), the FROC parameters (μ , Δ , β), the Kurtosis model parameters (D, K), and PI-RADS score.

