12.0 Statistical Considerations

As this is a single arm pilot study, no power analysis is necessary. Based on the PRECISION study, we expect a high grade PCa detection rate of approximately 30% or in 17/50 subjects (10). The primary outcome will be the comparison of the rate of high grade PCa detection based on the 2 possible MRI outcomes: men undergoing standard

12 core TRUS biopsy (detection protocol MRI negative) versus men undergoing MRI targeted biopsy (detection protocol MRI positive for lesions). This will be analysed for statistical difference using the chi-square test. Each MRI quantitative parameter will be evaluated on a per lesion basis as a predictor of high grade PCa using ROC logistic regression and will be reported as AUC with 95% confidence intervals (CI). The Youden's Index and 90% fixed sensitivity thresholds of each quantitative parameter will be reported. Combinations of MRI quantitative and clinical parameters will be combined into multinomial logistic regression models for which AUC with 95% CI will be reported. The AUC of the multi-parametric models will be compared iteratively for statistical differences using the likelihood ratio test.

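### The plan states no rule for calling the MRI positive and stores no PI-RADS read made before the quantitative maps, so detection cannot be cleanly credited to the quantitative analysis

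*Combined protocol and SAP*

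**What the plan says.** **What makes an MRI positive.** Five places bear on this.

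- Section 1.0 (Project Summary/Abstract) says the protocol "uses image collection and post-processing to assist the radiologist find areas of the prostate with increased suspicion for clinically significant cancer". It then says "men with suspicious MRI lesions (as defined by our preliminary data) will undergo biopsies of these lesions".
- Section 2.0 (Background) offers quantitative values as a supplement: "A detection specific protocol can be designed so that quantitative parameters can be measured as an adjunct to PI-RADS scoring". Later it gives them a larger role: "we propose to prospectively use quantitative DWI as a biomarker to determine regions of the prostate suspicious for high grade PCa".
- Section 3.0, Aim 2, says "Quantitative image analyses will be performed to generate SEM maps of DWI", and that suspicious areas are targeted. It does not say how a map value becomes a target.
- Section 5.0 (Study Design and Procedures) has the study team process the MRI, which is then "evaluated for areas suspicious for high grade PCa by a board certified clinical radiologist".
- Appendix 3 gives acquisition settings only.

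**How the call is used.** Section 12.0 compares high grade detection by chi-square between MRI-negative men, who have standard 12-core biopsy, and "men undergoing MRI targeted biopsy (detection protocol MRI positive for lesions". It reports Youden and 90%-sensitivity thresholds as results of the trial.

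**What is stored.** Section 8.0 lists a PI-RADS score, a lesion count, per-lesion summaries of each quantitative parameter, and lesion outlines on the T2 series. Section 5.0 (Study Design and Procedures) lists PI-RADS among the parameters whose accuracy is analysed secondarily.

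**The concern.** Two gaps act together.

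First, the variable that forms the primary groups has no operational definition in the text. Another site, or the next trial, could not repeat the test from what is written.

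Second, nothing requires PI-RADS to be scored before the maps are seen. The objective in section 3.0 is whether a protocol with quantitative analysis improves high grade detection. Section 2.0 hypothesises that quantitative tools help most with indeterminate studies, and cites a PI-RADS 3 false positive rate as high as 88%. Answering that requires the PI-RADS call as it stood without the maps. A PI-RADS score given with the maps in view is not an independent comparator for the SEM, FROC, kurtosis or ADC parameters. It may look better than PI-RADS alone would, which hides the added value, or it may simply move with them.

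**Working it through.** **1. The plan's own figure.** Section 12.0 expects about 30%, given as 17/50. The product is 50 × 0.30 = 15, while 17/50 = 34%. The difference of two men does not affect this point, and both rates are carried below. The plan gives no power calculation or positivity threshold to reproduce.

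**2. Is a rule stated anywhere?**

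| Place | Basis given for suspicion | Cut-off or combination rule |
|---|---|---|
| 1.0 | Preliminary data; post-processing helps the radiologist | None |
| 2.0 | Supplement to PI-RADS; also quantitative DWI | None |
| 3.0, Aim 2 | SEM maps generated, suspicious areas targeted | None |
| 5.0 (Study Design) | Radiologist evaluates processed MRI | None |
| 12.0 | MRI positive or negative, taken as given | Thresholds are outputs |

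The preliminary data in section 2.0 come from 31 men whose lesions were found by PI-RADS. The text gives no cut-off from them. Figures 2 and 4 were not available, so this finding concerns the text only.

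**3. Is there a read without maps?** Section 5.0 (Study Design) puts processing before evaluation. Section 8.0 sends image data from the scanner to the post-processing workstation and to the radiologist's workstation, and stores one PI-RADS score. No section hides the maps, sets the order of reading, or asks for an earlier score. The radiologist may in practice score PI-RADS first, but the plan neither requires nor records it.

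**4. Do the secondary analyses fill the gap?** Only partly. Section 12.0 evaluates each quantitative parameter per lesion. A lesion enters only if the combined read marked it, and men with no marked lesion contribute none. The AUCs therefore describe discrimination within a set the maps may have helped to select.

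**5. How much does the rule matter?** This is an illustration on assumed sensitivity (Se) and specificity (Sp), with high grade rate p, N = 50, and high grade disease ascertained equally in both groups.

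- Fraction positive: f = p·Se + (1 − p)(1 − Sp)
- Rate in MRI-positive men: p·Se / f
- Rate in MRI-negative men: p(1 − Se) / (1 − f)

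Lenient rule (0.95, 0.40), p = 0.30:
- f = 0.285 + 0.420 = 0.705, so 50 × 0.705 ≈ 35 positive and 15 negative
- rates 0.285/0.705 = 40.4% and 0.015/0.295 = 5.1%; contrast 35.3 points

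Strict rule (0.70, 0.85), p = 0.30:
- f = 0.210 + 0.105 = 0.315, so about 16 positive and 34 negative
- rates 0.210/0.315 = 66.7% and 0.090/0.685 = 13.1%; contrast 53.5 points

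At p = 0.34 the lenient rule gives f = 0.719, about 36 v 14 men, 44.9% v 6.0%, contrast 38.9 points. The strict rule gives f = 0.337, about 17 v 33 men, 70.6% v 15.4%, contrast 55.2 points.

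The group sizes and the contrast thus depend materially on a rule that is not written down.

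**The case against.** The best defence is that this is a pilot of one quantitatively assisted read. Section 1.0 says post-processing helps the radiologist, and section 5.0 has the radiologist read a processed MRI. On that view the test is the whole read, thresholds are properly results, and attribution to one ingredient is not the primary question. Much of this stands. The primary comparison can be run on the final call alone, and the per-lesion analyses do give some information. The defence does not supply the rule, however, or a PI-RADS score free of the maps.

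A reader might infer three stronger things that the documents do not support.

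- **That sections 1.0 and 5.0 give two rival definitions of positivity.** They can be read together as one assisted read. Section 1.0 speaks only of preliminary data; that these are quantitative is a fair inference from section 2.0. The fault is an unstated rule.
- **That an unfixed rule inflates the type I error of the chi-square test, or drifts as results arrive.** Inflation of that kind needs the cut-off to be chosen after the outcomes are known. Here each man's call precedes and directs his biopsy, and section 13.2 bars data analysis until accrual is complete and all data are de-identified. No section says biopsy results are fed back to the radiologist. Informal learning is not excluded, but it is conjecture.
- **That the quantitative contribution can never be learned, or that a fixed cut-off would reveal it.** The first is too absolute, given the planned AUCs. The second is wrong: with a single arm and a different biopsy method in each MRI group, even a fixed rule would not isolate the contribution through the primary comparison.

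**Conclusion.** The point holds in limited form. The text gives no operational rule for the call that forms the primary groups. The single stored PI-RADS score may carry information from the maps. The trial therefore cannot cleanly attribute detection to quantitative analysis beyond PI-RADS, and the per-lesion AUCs repair this only in part.

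On the assumed rules above, at 30% high grade disease, the MRI-positive group ranges from about 16 to 35 men and the contrast from about 35 to 54 points. These figures show sensitivity to the rule; they do not estimate bias. That PI-RADS is contaminated is a possibility the plan leaves open, not a demonstrated fact. The conclusion also assumes that the missing figures contain no reading rule; section 12.0 makes that likely by treating thresholds as outputs. This is a cheap improvement and does not invalidate the pilot.

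**What to change.** In sections 5.0 (Study Design and Procedures), 8.0 and 12.0:

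1. **Step 1.** The radiologist records and locks in REDCap the PI-RADS score and lesion outlines before opening the quantitative maps.
2. **Step 2.** The same radiologist then records the final call with the maps. MRI-positive in the primary comparison means positive at step 2.
3. Write the step 2 reading rule before enrolment: which inputs are used and how maps and PI-RADS are combined. A numeric SEM cut-off is optional. One taken from 31 men with PI-RADS-selected lesions would be imprecise.
4. Use the step 1 score in the PI-RADS accuracy analysis and as the comparator for the quantitative parameters.
5. Report how many men and lesions changed call between steps, with high grade results among those sampled. State that lesions seen only at step 1 can be assessed only where cores were taken.

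Sections 1.0 and 5.0 differ on whether MRI-positive men have systematic as well as targeted cores. Those passages must be reconciled separately, and nothing here depends on how.

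The cost is two REDCap entries and a few extra minutes per read, with no added reader, scan or biopsy. The gain is a PI-RADS comparator free of the maps and a before-and-after record. It does not turn the single-arm comparison into a test against conventional practice.

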2.0 Background/Scientific Rationale

While there is concern for over-treatment of prostate cancer (PCa) it remains the 2nd leading cause of cancer death in U.S. men (1). This paradox is due in part to the accuracy limitations of current detection methods of serum prostate specific antigen (PSA) and digital rectal examination (DRE) screening, and the inability of current clinical information to discriminate indolent from aggressive tumors. Clinical patient characteristics including age, race, family history of PCa, DRE, and prior negative prostate biopsy history have been combined into a predictive calculator to guide biopsy decisions(2). Men found to have adequate suspicion for PCa require a tissue diagnosis. Standard PCa detection relies on 12-core transrectal ultrasound (TRUS) guided biopsy that samples anatomic zones of the prostate gland. Approximately 35% of men undergoing immediate radical prostatectomy (RP) for low grade PCa on standard biopsy will be found to have higher grade tumors in the pathologic specimen(3). Furthermore, between 30-38% of men with clinical suspicion for PCa and a negative standard biopsy will be diagnosed with PCa on re-biopsy(4). Finally, TRUS biopsy is an invasive procedure with a rate of sepsis as high as 2%, and this risk is proportional to the number of biopsy cores sampled(5). With a more precise method for early detection of the most aggressive tumors, men with indolent PCa could be spared treatment with its associated cost and morbidities and instead be managed conservatively with active surveillance (AS), while those with potentially lethal disease could be expediently referred for radiation or surgery with curative intent.

Improved PCa detection may be particularly important for African American (AA) men, who are almost twice as likely to die from PCa as white men(1). A recent study of men with very low risk PCa based on clinical information who underwent immediate RP found that AA men were more likely to have adverse RP pathology and anteriorly located tumors not reached with standard TRUS prostate biopsies(6). In addition, two series of men selected for AS based on standard clinical information reported that AA men progressed to treatment faster than white men(7, 8). These data have questioned the safety of managing AA men with AS without more accurate risk stratification tools such as imaging. At UIC, over 60% of PCa cases diagnosed are in AA men.

[figure not shown]
Standard TRUS imaging does not provide enough resolution to localize most PCa, much less provide information about its aggressiveness. One promising approach to improve PCa detection and risk stratification is through advanced imaging such as magnetic resonance imaging (MRI). In this setting an ideal imaging study would differentiate aggressive PCa from indolent PCa and benign processes such as hyperplasia (BPH) or inflammation as well as localize the aggressive PCa to reduce biopsy sampling error. Currently in the US, prostate mpMRI is approved for : 1) men with continued suspicion for PCa but negative TRUS biopsy or 2) for staging of known high risk PCa for treatment planning. The images from the mpMRI can be used for

[figure not shown]
targeted biopsies using TRUS/mpMRI imaging fusion to improve PCa detection(9). As such, there is interest in using mpMRI as a confirmatory test in men with elevated PSA and prior to the first biopsy to improve biopsy accuracy and potentially obviate the need for unnecessary “random” biopsies. A landmark study conducted in Europe, the PRECISION trial, recently reported that TRUS/mpMRI fusion biopsies in biopsy naive men with suspected PCa resulted in an increase in the absolute detection of clinically significant PCa of 12% in men randomized to mpMRI, despite 28% of the men in this group avoiding biopsy due to a negative study(10). These data are certainly compelling, but have yet to be replicated in a US population, and particularly in a high-risk group such as AA men. The implications in the US are significant as approximately 1 million TRUS biopsies are performed annually for known or suspected PCa(11).

While MRI protocols are variable and evolving, the current recommended standard is combining T2-weighted anatomical imaging (T2WI) with two functional MRI techniques, typically diffusion-weighted images (DWI) and dynamic contrast enhanced images (DCE), together to create a multi-parameter MRI (mpMRI) study. A radiologist reviews the imaging and assigns a semi-qualitative suspicion of high grade PCa on a 1-5 Likert scale. This score, called the prostate imaging reporting and data system (PI-RADS), is an attempt to standardize mpMRI assessment and guide clinical management(12).

The PI-RADS has several limitations including modest inter-rater reliability(13, 14), and a false positive rate of as high as 88% of the PI-RADS 3 (indeterminate) scores (figure 1). Currently the same prostate MRI protocols are used for PCa detection in men with prior negative TRUS biopsies, staging of known PCa, and for suspected PCa local recurrence after treatment. As such, the protocol contains several imaging sequences such as T1 weighted imaging to detect hemorrhage related to biopsy and DCE which is of limited value for PCa detection which add to the study time and cost(15). In addition, the fields of view of prostate MRI protocols are designed to show surrounding structures such as the pelvic lymph nodes for staging purposes which aren't applicable to the primary PCa detection setting. These larger fields of view come at the expense of longer study times, and lower imaging detail in the prostate.

Finally, current prostate MRI protocols are designed for qualitative assessment and PI-RADS scoring. A detection specific protocol can be designed so that quantitative parameters can be measured as an adjunct to PI-RADS scoring. We hypothesize that quantitative tools for image assessment could benefit radiologists to further characterize indeterminate MRI studies, and to facilitate comparisons across patients, centers, and populations.

Our study explores 2 ways to improve mpMRI for PCa detection: 1) Developing an imaging protocol specifically designed for biopsy naïve men with suspected PCa and 2) improving utility of the collected images with quantitative image analysis tools as an adjunct to PI-RADS. DWI characterizes the Brownian movement of water molecules in tissues. Conventional DWI fits a line to data acquired using two strengths (b-values) of the magnetic diffusion gradient, the slope of which is the apparent diffusion coefficient (ADC) which can be used as a quantitative parameter.

When compared to RP histology, ADC has a moderate inverse correlation with PCa grade (ref ADC and grade). With conventional DWI the calculation of ADC assumes a gaussian distribution of water molecule diffusion and tissue homogeneity which may oversimplify water motion in organs with complex tissue structures. A technique that more accurately determines water diffusion through tissues may better discriminate cancer grade. As such, we have tested stretched exponential (SEM) and kurtosis models of DWI with high b-values to determine the grade of PCa in 31 men undergoing biopsy targeted to MRI lesions identified using standard PI-RADS scoring. We found accuracy as measured by area under the receiver operator curve (AUC) that is significantly improved over PI-RADS, the PBCG model, and modestly improved over conventional ADC (Figure 2). Therefore, we propose to prospectively use quantitative DWI as a biomarker to determine regions of the prostate suspicious for high grade PCa in biopsy naïve men.

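### Section 12 plans no paired comparison of non-Gaussian DWI parameters with conventional ADC, although that gain is part of the DWI rationale

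*Combined protocol and SAP*

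**What the plan says.** Section 2.0 (Background/Scientific Rationale) describes conventional ADC as a fit to two b-values that may oversimplify diffusion in complex tissue, and continues: "A technique that more accurately determines water diffusion through tissues may better discriminate cancer grade". It then reports stretched exponential (SEM) and kurtosis models in 31 men. Their AUC was significantly better than PI-RADS and the PBCG model, and against ADC only "modestly improved over conventional ADC (Figure 2". The AUC values are in a figure that is not reproduced. On these results the protocol adopts quantitative DWI. Section 3.0 specifies b-values up to 4000 and SEM maps, and Appendix 3 lists 11 b-values.

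Section 5.0 (Study Design and Procedures) makes parameter accuracy a secondary analysis: "Secondarily we will analyze the accuracy of the individual MRI parameters including: T2 imaging, ADC, the SEM parameters", followed by the FROC and kurtosis parameters and PI-RADS. ADC is one entry in that list, not a named comparator.

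Section 12.0 states: "Each MRI quantitative parameter will be evaluated on a per lesion basis as a predictor of high grade PCa using ROC logistic regression". The output for each "will be reported as AUC with 95% confidence intervals (CI"), with thresholds. The only comparison of AUCs is among multi-parametric models, made iteratively by likelihood ratio test. The models are not listed and no reference model is named.

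**The concern.** SEM and ADC are computed from the same diffusion series in the same lesions, so their AUC estimates should be strongly and positively correlated. Two separate intervals discard that correlation. This can mislead in two directions. A real gain can be dismissed because two wide intervals overlap, or the non-Gaussian parameter with the highest point estimate can be called better than ADC with no interval for the difference behind it.

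The planned likelihood ratio test does not fill the gap. It asks whether adding terms improves the fit of a nested model. It cannot set SEM alone against ADC alone, and it returns neither an AUC difference nor a CI. At stake is what the pilot can say about whether the richer diffusion model adds to conventional ADC, which is part of the case for the multi-b, high-b acquisition.

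**Working it through.** **The plan's own figure.** Section 12 expects about 30% high grade cancer, or 17/50. 0.30 × 50 = 15, while 17/50 = 34%. Both counts are used below. The plan states no AUC target, power, lesion count or between-parameter correlation, so those are assumptions.

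**Step 1: analytic check.** Assume one lesion per man, m = 17 high grade and n = 33 other, AUC 0.75 (ADC) and 0.80 (new parameter). The Hanley-McNeil variance is [A(1−A) + (m−1)(q1−A²) + (n−1)(q2−A²)]/(mn), with q1 = A/(2−A) and q2 = 2A²/(1+A).

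- A = 0.75: q1 = 0.600, q2 = 0.643; variance = (0.1875 + 16 × 0.0375 + 32 × 0.0804)/561 = 0.00599; SE = 0.077; 95% CI 0.60 to 0.90.
- A = 0.80: q1 = 0.667, q2 = 0.711; variance = (0.16 + 16 × 0.0267 + 32 × 0.0711)/561 = 0.00510; SE = 0.071; 95% CI 0.66 to 0.94.

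These two intervals, the form of output now planned, overlap almost entirely.

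For the difference, SE = √(s1² + s2² − 2r·s1·s2) = √(0.01109 − 2r × 0.00553), where r is the correlation between the two AUC estimates. Power is Φ(0.05/SE − 1.96).

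| r | 95% half-width | power for 0.05 |
|---|---|---|
| 0 (pairing ignored) | 0.206 | 7% |
| 0.5 | 0.146 | 10% |
| 0.7 | 0.113 | 14% |
| 0.9 | 0.066 | 32% |

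**Step 2: simulation.** Two correlated binormal markers, DeLong variances and covariances, 3,000 data sets per setting, within-lesion correlation of marker values 0.6 to 0.9 (a different scale from r above). The smaller lesion count uses the 28% MRI-negative share that section 2.0 cites from an outside trial: 0.72 × 50 = 36 men with lesions, and 36 − 15 = 21.

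| Lesions (high grade vs other) | True AUCs | Paired half-width | Pairing ignored | Paired power |
|---|---|---|---|---|
| 15 vs 35 | 0.85 vs 0.75 | 0.08–0.13 | 0.19 | 31–73% |
| 15 vs 21 | 0.85 vs 0.75 | 0.09–0.15 | 0.21 | 26–60% |
| 15 vs 35 | 0.80 vs 0.75 | 0.08–0.14 | 0.20 | 11–22% |
| 15 vs 21 | 0.80 vs 0.75 | 0.09–0.15 | 0.22 | 9–16% |

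In the first row at correlation 0.8, the paired half-width is 0.10 against 0.19, and the difference is detected in 48% of data sets with pairing and 4% without. Separate 95% CIs fail to overlap in at most 1.5% across the correlation range. A repeat of the simulation agreed with the table to within about 2 percentage points of power.

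**Limits.** Several lesions per man, and clustering of lesions within men, are not modelled. The 15 to 17 high grade cases are counts of men, and some may be found only on systematic biopsy after a negative MRI, so the number of high grade target lesions could be lower; multiple lesions per man could raise it.

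**The case against.** A reader might infer that the whole trial rests on SEM beating ADC and leaves that hypothesis untested. The documents do not support this. The stated purpose concerns the complete protocol: "This study aims to determine whether a detection specific MRI protocol with quantitative image analysis can improve high grade PCa detection". The sentence worded as a hypothesis concerns an adjunct to PI-RADS: "We hypothesize that quantitative tools for image assessment could benefit radiologists to further characterize indeterminate MRI studies". The primary outcome is the high grade detection rate by MRI result. The comparison with ADC is one of three in the background and the weakest of them. All of this stands, and it limits the point to a secondary analysis.

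Nor is the question wholly outside the plan. A nested comparison of ADC with ADC plus DDC and α would fall within section 12's wording and would address added value. But the plan does not name that comparison, and it would still give no AUC difference.

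It is also fair to say that a 50-man pilot cannot settle a modest gain: for 0.80 against 0.75, the paired test would miss it about four times in five or more. That stands, and it is why the contrast should be estimation.

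Finally, SEM maps are generated before targeting, so selection could distort the contrast, perhaps against SEM. A simple binormal check with selection on SEM did not bear out that direction: both AUCs fell, and in most settings ADC fell more. The direction is therefore not established, and the restriction to targeted lesions needs stating.

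**Conclusion.** The gap holds as a secondary-analysis omission. The background gives the gain over ADC as part of the reason for the diffusion method, yet section 12 plans no estimate of that gain. Over the assumed inputs (15 high grade and 21 to 35 other lesions, within-lesion correlation 0.6 to 0.9), pairing brings the 95% half-width to about 0.08 to 0.15, from 0.19 to 0.22. The exact size depends on those assumptions; the direction needs only a positive correlation, which is expected for parameters from one acquisition in the same lesions.

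Two stronger readings should be set aside: that the trial's main question goes unanswered, and that a paired test would resolve the SEM-versus-ADC question. Power of about 9% to 22% for a 0.05 gain rules out the second. The improvement is a usable interval for planning a later study.

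**What to change.** Add to section 12 one named secondary contrast: AUC of SEM (DDC) minus AUC of conventional ADC in the same lesions, with a paired 95% CI from a bootstrap that resamples men, since the analysis is per lesion and lesions cluster within men. State which b-values define conventional ADC; section 2.0 describes a two-b-value fit. Report kurtosis-minus-ADC and FROC-minus-ADC the same way, labelled supportive. Say that these are estimates, not confirmatory tests, and that they apply to lesions selected for targeting.

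The cost is a few sentences of analysis plan and a few lines of code, with no new data. Section 13.2 bars analysis until accrual is complete, so the contrast can be fixed before any results are seen. The downside for the investigators is that the advantage over ADC may turn out not to be supported.
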